1. LIST OF ABBREVIATIONS

ACE	Angiotensin-Converting-Enzyme inhibitor
ADR	Adverse Drug Reaction
ARNI	Angiotensin Receptor-Neprilysin Inhibitor
AE	Adverse Event
BI	Boehringer Ingelheim
BMI	Body mass index
BNP	Brain Natriuretic Peptide
CCB	Calcium Channel Blocker
CHF	Chronic Heart Failure
CI	Confidence Interval
CRF	Case Report Form
CV	Cardiovascular
DPP-IV	Dipeptidyl Peptidase IV
EDC	Electronic Data Capture
eGFR	estimated Glomerular Filtration Rate
EoT	End-Of-Text
E peak	Early diastolic left ventricular filling velocity
e'	Early diastolic mitral annular velocity
GLP-1	Glucagon - Like Peptide 1
HF	Heart Failure
LAD	Left atrial dimension
LVEDD	Left ventricular end-diastolic diameter
LVEF	Left ventricular ejection rate
LVESD	Left ventricular end-systolic diameter
MedDRA	Medical Dictionary for Drug Regulatory Activities
MRA	Mineralocorticoid Receptor Antagonist
NIS	Non-interventional study
NT-proBNP	N-Terminal pro-Brain Natriuretic Peptide
NYHA	New York Heart Association functional classification
PD	Protocol deviation
PMS	Post Marketing Surveillance
PT	Preferred term
RMP	Risk Management Plan
SAE	Serious Adverse event
SEAP	Statistical and epidemiological analysis plan
SMQ	Standardized MedDRA query
SOC	System organ class
T2DM	Type 2 Diabetes mellitus

2. RESPONSIBLE PARTIES

Contact details and the list of all investigators will be kept in a stand-alone document. This document will be managed in the Post Marketing Surveillance (PMS) tracking system which manages the contracts with site and investigators name.

3. PURPOSE AND SCOPE

The purpose of this document is to provide a more technical and detailed elaboration of the principal features of the analysis described in the protocol, and to include detailed procedures for executing the statistical analysis of the PMS data.

This SEAP assumes familiarity with the Non-interventional Study (NIS) Protocol, including Protocol Amendments. In particular, the SEAP is based on the planned analysis specification as written in NIS Protocol Section 9.7 “DATA ANALYSIS”. Therefore, SEAP readers may consult the NIS Protocol for more background information on the study, e.g., on study objectives, study design and population, treatments, definition of measurements and variables, planning of sample size.

4. AMENDMENTS AND UPDATES

Number	Date	Section of study protocol	Amendment or update	Reason
None				

5. RESEARCH QUESTION AND OBJECTIVE

The primary objective is to evaluate the incidence of adverse drug reaction (ADR) (focus on hypoglycaemia, the events relevant volume depletion, influence of ketone body increased / ketoacidosis, renal impairment) of JARDIANCE Tablets under the real world setting in patients with CHF (Chronic Heart Failure).

6. RESEARCH METHODS

6.1 STUDY DESIGN

This is a non-interventional study based on newly collect data of patients under routine care to confirm safety and effectiveness of JARDIANCE® Tablets in real-world setting in Japanese patients with CHF.

6.2 SETTING

6.2.1 Study sites

Sites throughout entire country will be equally listed according to the size of the hospitals or general clinics at which JARDIANCE® Tablets are available for prescription.

Planned number of sites: Approximately 200 Sites (including CV (Cardio vascular) internal medicine)

A medical representative will explain the objective and design of this study to investigators at each study site and conclude a written contract with the head of the study site (e.g., hospital director).

6.2.2 Inclusion/ exclusion criteria

Inclusion criteria

- Patients with CHF who are prescribed with JARDIANCE® Tablets in Japan.
- Patients who have never been treated with Empagliflozin (including treatment for Type 2 Diabetes mellitus (T2DM)) before enrolment.

Exclusion criteria

None

6.2.3 Registration period

From April 2022 to March 2023

6.2.4 Patient registration method

The registration method will be a central registration system. Patients who begin treatment with JARDIANCE® Tablets after the conclusion of the contract will be registered by entering necessary information in the Electronic Data Capture (EDC) system within 14 days from the day of treatment initiation (inclusive).

Patient registration will be stopped when the overall target number of patients for the study is reached.

6.3 STUDY POPULATION

The following table defines the different categories of important Protocol Deviations (iPDs). The final column describes which iPDs will be used to exclude patients from each patient analysis sets. The final decision about which patients will be excluded from analysis sets will be taken during the study and at report planning meetings before database lock at the latest.

Table 6.3: 1 Important protocol deviations

Category / Code	Description	Requirements	Method	Excluded from
A	Entrance criteria not met			
A1.1	Patient of non-CHF	Reason for use is not CHF	Automated	Effectiveness
A1.2	Patient received Empagliflozin (JARDIANCE®) or Empagliflozin + Linagliptin (TRADIANCE®) treatment before registration	See Previous Medication code*:3969023, 3969108	Automated	All
C	Trial medication and randomization			
C1	Incorrect trial mediation taken			
C1.1	No treatment with JARDIANCE® Tablets	No treatment status	Automated	All
G	Trial specific			
G1	Invalid registration			
G1.1	No patient visits after entry	Administration status is “No visit since the first visit”	Automated	All
G1.2	Duplicated registration	Patient who has been already registered in this study with another patient ID. In this case, all data for the later patient will not be used.	Manual	All
G1.3	Registration rule not followed	Patient registered beyond 14 days since the administration of JARDIANCE® started. (See NIS Protocol section 9.2.2.1)	Automated	All
G1.4	Patient started JARDIANCE® treatment out of registration period	Patient started JARDIANCE® treatment out of registration period. (See NIS Protocol section 9.2.2.1)	Automated	All
G1.5	Patient started JARDIANCE® treatment out of contract period for each site	Patient started JARDIANCE® treatment out of contract period for each site. (See NIS Protocol section 9.2.2.1)	Manual	All

Note *Previous Medication code is coded by latest version of “Nihon-iyakuhinshu”.

The safety set will be the basis of all demographics, baseline and safety analyses. Effectiveness analysis will be on basis of the effectiveness set.

- Safety set:

This patient set includes all patients who didn't have iPDS regarding safety and regulatory issues as marked as "All" in [Table 6.3: 1](#).

- Effectiveness set:

This patient set includes all patients in safety set with CHF and have effectiveness information. (Patients marked "Effectiveness" in [Table 6.3: 1](#) should be excluded from effectiveness analysis.)

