6.4 STUDY VISITS

The study will consist of a baseline visit and further visits in a 52-week follow-up for patients who have initiated JARDIANCE® Tablets treatment. The follow-up data (safety and administration of JARDIANCE®) from patients who change hospital and continue taking JARDIANCE® will be collected by participating investigators if possible.

With regard to effectiveness and safety endpoints, the term "baseline" refers to the last observed measurement before the first administration of JARDIANCE® Tablets. The first date of the administration of JARDIANCE® Tablets is included in "baseline".

The analyses of eGFR over time will be performed based on calculated visits as shown in [Table 6.4: 1](#). If two or more data points of a patient fall into the same interval, the closest value to the planned day will be selected. If there are two observations which have the same difference in days to the planned day or if there are two observations on the same day, the first value will be used.

Table 6.4: 1 Baseline, time windows and calculated visits

Week label	Planned days	Time window (actual days on treatment)	
		Start	End
Baseline	1	The last observed measurement before administration of JARDIANCE®	
Week 12	84	2	133
Week 26	182	134	231
Week 40	280	232	322
Week 52	364	323	End of study

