7. VARIABLES

7.1 EXPOSURES

Exposure to JARDIANCE® Tablets is estimated as time from the day JARDIANCE® Tablets is initiated until the day the drug is last administrated on a patient-level (or the final contact with the patient during the regular observation period).

Patients newly initiating JARDIANCE® Tablets will be followed up to 52 weeks.

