10.3.1 Adverse events

Unless otherwise specified, the analyses of adverse events (AEs) will be descriptive in nature. All analyses of AEs will be based on the number of patients with AEs and NOT on the number of AEs.

All AEs occurring between the initiation of JARDIANCE® Tablets prescribed at baseline visit and 7 days (inclusive) after the last administration will be considered ‘treatment emergent’.

Furthermore, for analysis of AE attributes such as duration, severity, etc. multiple AE occurrence data on the CRF will be collapsed into AE episodes provided that all of the following applies:

- The same MedDRA lowest level term was reported for the occurrences.
- The occurrences were time-overlapping or time-adjacent (time-adjacency of 2 occurrences is given if the second occurrence started on the same day or on the day after the end of the first occurrence).
- Treatment did not change between the onset of the occurrences OR treatment changed between the onset of the occurrences, but no deterioration was observed for the later occurrence.

For further details on summarization of AE data, please refer to BI standards (‘Analysis and Presentation of Adverse Event Data from Clinical Trials’ [\(2\)](#)).

Unless otherwise specified, AE analyses will be used AE data from safety database.

An Adverse Drug reaction (ADR) is defined as an AE for which either the investigator or the sponsor (or both) assesses the causal relationship to JARDIANCE® as “Yes.” A serious AE is defined as an AE for which either the investigator or the sponsor (or both) assesses the seriousness as “Serious.”

The SOCs will be sorted according to the standard sort order specified by European medicines agency. PTs will be sorted by frequency (within SOC).

The frequency of patients with the following items will be summarized.

- AEs
- ADRs
- Severe AEs
- Severe ADRs (Dr)
- AEs leading to discontinuation
- ADRs (Dr) leading to discontinuation
- AEs leading to all-cause death
- ADRs leading to all-cause death
- AEs leading to CV death
- ADRs leading to CV death
- AEs leading to hospitalization for HF
- ADRs leading to hospitalization for HF
- Serious AEs
- Serious ADRs

Note1: Severe AEs/ADRs and AEs/ADRs leading to discontinuation will be used AE data from CRF.

Note2: For the definition of all-cause death, CV death and HF, refer to note in Section [10.2.5](#).

Note3: ADRs (Dr) is defined as an AE for which only the investigator assesses the causal relationship to JARDIANCE® as “Yes”.

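### The duplicate-registration rule (Table 6.3: 1, G1.2) discards everything under the later ID instead of linking it to the first, so safety data held only there are lost for a patient who stays in the safety set

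*SAP*

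**What the plan says.** Section 6.3, Table 6.3: 1 lists duplicate registration as G1.2, under invalid registration. The case is described as "Patient who has been already registered in this study with another patient ID", so the two IDs belong to one person. The instruction is: "In this case, all data for the later patient will not be used". The check is manual and the exclusion applies to all analysis sets. G1.2 does not exclude the first record, and the table has no step for carrying information from the later ID to the first.

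Two other sections fix the unit of analysis. Section 7.1 runs exposure from initiation "until the day the drug is last administrated on a patient-level", or to the final contact in the regular observation period. Section 10.3.1 states: "All analyses of AEs will be based on the number of patients with AEs and NOT on the number of AEs". Both work per patient, not per ID.

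Section 6.4 adds that safety and administration data "from patients who change hospital and continue taking JARDIANCE® will be collected by participating investigators if possible".

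**The concern.** The primary endpoint is ADR incidence, shown as a frequency and a proportion with its confidence interval (sections 7.2.1 and 10.1). A rule that removes recorded safety information on a treated patient, while that patient stays in the denominator, acts directly on this endpoint. G1.2 settles a question about IDs (which one stands for the patient) by a step that also deletes information about the patient. The two need not go together.

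On average the stake is small. It matters more for the uncommon focus events, such as ketoacidosis, where one discarded case can separate none observed from one observed. Lost dosing dates matter too. Section 10.3.1 treats an event as treatment-emergent up to 7 days after the last administration, so a last dose known only from the later ID would extend that window.

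**Working it through.** The SAP gives no number of duplicates, ADR rate or figure of its own on this point. The check is therefore a comparison of its sections, followed by an illustrative bound.

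**Step 1: what happens to a patient with two IDs under the literal rule**

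| Item | Under the first ID | Only under the later ID |
|---|---|---|
| Patient in the safety set | Yes, once (not excluded by G1.2) | Not counted again (correct) |
| ADR | Counted | Lost |
| Death or heart failure hospitalisation | Counted | Lost |
| Dosing dates and exposure time | Used | Lost |

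If the later record only repeats the first, nothing is lost. If it holds something new, the patient's adverse event status or exposure is wrong by the SAP's own patient-level definitions.

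**Step 2: direction for the simple ADR proportion**

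Let N be the number of distinct patients, d the share registered twice, and q the share of those whose only ADR is recorded under the later ID. With linked records the proportion is A/N, where A is the number of patients with at least one ADR. Under G1.2 as written:

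(A − d·q·N)/N = A/N − d·q

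The denominator does not change, so the shift is −d·q. It is zero or negative, never positive.

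**Step 3: size of that shift**

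Both inputs are assumptions: d from 0.1% to 2%, q from 5% to 20%.

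- Low end: 0.001 × 0.05 = 0.00005, or 0.005 percentage points (0.05 patients per 1,000).
- High end: 0.02 × 0.20 = 0.004, or 0.4 percentage points (4 patients per 1,000).

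**Step 4: direction for exposure-adjusted rates**

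Section 10.3.2 also plans incidence rates adjusted for treatment exposure, for deaths, first heart failure hospitalisation and the safety specifications. Let E be the events and T the exposure time with linked records, of which e and t come only from later IDs. The rate under G1.2 is (E − e)/(T − t). This lies below E/T when e/t exceeds E/T, and above it when e/t is smaller. The direction is therefore not fixed.

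**Step 5: is there a conflict with section 6.4?**

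Section 6.4 asks for continued data on patients who change hospital, where possible. It mentions no second registration. Other rules point away from one:

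- Section 6.2.2 admits only "Patients who have never been treated with Empagliflozin" before enrolment.
- Section 6.2.4 registers patients who are starting treatment, within 14 days of initiation.
- A1.2 excludes from all sets a "Patient received Empagliflozin (JARDIANCE®) or Empagliflozin + Linagliptin (TRADIANCE®) treatment before registration".
- G1.3 excludes from all sets a "Patient registered beyond 14 days since the administration of JARDIANCE® started".

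A patient already on drug who moves to another site is thus not meant to be registered anew. Follow-up under the first ID fits the text.

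**The case against.** The strongest reply is that G1.2 is ordinary de-duplication. It prevents one patient from entering the denominator twice, and it loses information only if the later record holds something that the first lacks. The check is manual, and section 6.3 leaves final exclusions to meetings before database lock, so a careful team could notice a unique event. Section 8 requires adverse events to be entered and transmitted at once, so the rule touches the analysis and not the reporting of events. Reconciling records between sites is also often settled in data management procedures that are not at hand.

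Most of this stands, and it limits the point. It does not remove it. The SAP is not merely silent here: its instruction covers all data under the later ID and provides for no exception. The meetings decide which patients leave an analysis set, and nothing in the text lets them move data from one ID to another.

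A reader might infer more: that G1.2 undoes the aim of following patients who change hospital, because a move would commonly produce a second ID. The documents do not support this. Section 6.4 does not rely on a new registration and is qualified by feasibility, the entry rules do not allow a patient on drug to be newly registered, and nothing states how duplicates usually arise. A conflict would arise only if the new site registered the patient again against the rules and entered the follow-up only there. A1.2 and often G1.3 would then also exclude the later ID, so deleting the G1.2 sentence alone would not save those data.

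**Conclusion.** The point holds as a minor one. G1.2 rightly counts a doubly registered patient once, but as worded it also discards any ADR, outcome or dosing date recorded only under the later ID. That is at odds with the patient-level definitions in sections 7.1 and 10.3.1.

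The loss depends on the later record holding unique information. The downward direction is certain only for the simple ADR proportion, compared with linked records; it should not be claimed for the rates in section 10.3.2. The range in the working rests wholly on assumed shares of duplicates and of unique ADRs, and the effect is probably small. No contradiction between G1.2 and section 6.4 is shown.

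**What to change.** Amend G1.2 in Table 6.3: 1 to say that:

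- the patient is analysed once, under the first ID, and the later ID is excluded as a separate patient;
- adverse events, dosing dates and outcomes found only under the later ID, and falling within the patient's observation period, are linked to the first ID after repeated entries are removed;
- the number of duplicate registrations is reported.

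The link should also be made in the safety database, from which section 10.3.1 draws most adverse event analyses. It should be stated as part of G1.2 itself, so that A1.2 and G1.3 are understood to exclude the later ID as a patient without blocking the transfer of its data.

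The cost is a sentence or two in the table and manual linking of a few records, at a check that is already manual. The one risk is counting a repeated entry twice, which the removal of repeats and the patient-level counting both contain.

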6.4 STUDY VISITS

The study will consist of a baseline visit and further visits in a 52-week follow-up for patients who have initiated JARDIANCE® Tablets treatment. The follow-up data (safety and administration of JARDIANCE®) from patients who change hospital and continue taking JARDIANCE® will be collected by participating investigators if possible.

With regard to effectiveness and safety endpoints, the term "baseline" refers to the last observed measurement before the first administration of JARDIANCE® Tablets. The first date of the administration of JARDIANCE® Tablets is included in "baseline".

The analyses of eGFR over time will be performed based on calculated visits as shown in [Table 6.4: 1](#). If two or more data points of a patient fall into the same interval, the closest value to the planned day will be selected. If there are two observations which have the same difference in days to the planned day or if there are two observations on the same day, the first value will be used.

Table 6.4: 1 Baseline, time windows and calculated visits

Week label	Planned days	Time window (actual days on treatment)	
		Start	End
Baseline	1	The last observed measurement before administration of JARDIANCE®	
Week 12	84	2	133
Week 26	182	134	231
Week 40	280	232	322
Week 52	364	323	End of study

7. VARIABLES

7.1 EXPOSURES

Exposure to JARDIANCE® Tablets is estimated as time from the day JARDIANCE® Tablets is initiated until the day the drug is last administrated on a patient-level (or the final contact with the patient during the regular observation period).

Patients newly initiating JARDIANCE® Tablets will be followed up to 52 weeks.

7.2 OUTCOMES

[figure not shown]
7.2.1 Primary outcomes

The primary endpoint of this study is the incidence of ADRs (focus on hypoglycaemia, the events relevant volume depletion, influence of ketone body increased / ketoacidosis and renal impairment).

There is no primary outcome for effectiveness as the primary objective of a PMS is evaluating safety.

7.2.2 Secondary outcomes

- Incidence of all-cause death
- Incidence of CV death
- Incidence of hospitalizations for heart failure

7.3 COVARIATES

The covariates included in the model analysis are described at [Table 10.3.1: 1](#) in [Section 10.3](#).

8. DATA SOURCES

Case Report Forms (CRFs) for individual patients will be provided by the sponsor via the EDC system.

In EDC system, two casebooks will be set:

Book 1 includes baseline, 12 weeks and 26 weeks.

Book 2 includes 40 weeks and 52 weeks.

The data are to be transmitted immediately after being entered into EDC at 26 weeks (Book 1) and 52 weeks (Book 2) after the start of treatment or at discontinuation.

For any adverse events, the data should be immediately entered into EDC and transmitted.

9. DATA MANAGEMENT AND SOFTWARE / TOOLS

9.1 SOFTWARE/TOOLS

SAS® Version 9.4 or later will be used for all analyses.

9.2 HANDLING OF MISSING VALUES

Safety:

Missing or incomplete AE dates are imputed according to BI standards (see “Handling of missing and Incomplete AE dates” ([1](#)))

Missing or partial date information will be replaced according to following rules.

YEAR	MONTH	DAY	YMD	DT
“Unknown” (tick-box)			UNKNOWN	.
yyyy	Null or “Unknown”	Null	yyyy	yyyy/01/01
yyyy	mm	Null or “Unknown”	yyymm	yyyy/mm/01

In general, when tabulating AEs, and demographic and baseline characteristics variables reported as unknown will be treated as such; otherwise treated as missing data.
eGFR, Blood pressure (Systolic blood pressure and Diastolic blood pressure), Pulse rate, Weight, Grip Strength and Echocardiography (LVEF, LVEDD, LVESD, LAD, E peak, A peak and e'): For the missing values in these items, no imputation methods will be employed.

9.3 HANDLING OF INCONSISTENCIES IN DATA AND OUTLIERS

Outliers will not be excluded from analyses unless otherwise noted.

10. DATA ANALYSIS

For End-Of-Text (EoT) tables, the set of summary statistics is: N / Mean / SD / Min / Q1 / Median / Q3 / Max.

[figure not shown]
For tables that are provided for endpoints with some extreme data, median, quartiles and percentiles should be preferred to mean, standard deviation, minimum and maximum.

[figure not shown]
Tabulations of frequencies for categorical data will include all possible categories and will display the number of observations in a category as well as the percentage (%) relative to the respective treatment group (unless otherwise specified, all patients in the respective patient set whether they have non-missing values or not). Percentages will be rounded to two decimal places. The category missing will be displayed only if there are actually missing values.

[figure not shown]
10.1 MAIN ANALYSIS

[figure not shown]
The analysis of the primary outcomes is described in [Section 10.3.1](#).

[figure not shown]
In this PMS, since the primary endpoint is the incidence of ADRs (focus on hypoglycaemia, the events relevant volume depletion, influence of ketone body increased / ketoacidosis and renal impairment), the main analysis is to show frequency, proportion and its corresponding confidence interval (CI). The details are given in [Section 10.3.1](#).

[figure not shown]

[figure not shown]

[figure not shown]

